9.2. Analysis of Outcome Measures

Completion of the task will be defined as spending at least £5 on products from the target categories.

Primary Analysis

Linear regression models will compare the total energy (kcal) purchased in the two groups. Any baseline variables (e.g. demographic characteristics) which appear to have been imbalanced between groups will be adjusted in the model.

Secondary Analysis

Linear regression models will compare the (i) total sugar (g, kcal, %E), (ii) total salt (g, kcal, %E) and (iii) total SFA (g, kcal, %E) purchased in the two groups.

Secondary analyses will also compare differences in total energy (kcal), total sugar (g, kcal, %E), total salt (g, kcal, %E) and total SFA (g, kcal, %E) across the individual target categories.

We will also conduct secondary analyses of the primary and secondary outcomes specified above by gender, age group, ethnic group (White vs Non-White), BMI stratified into <30 and ≥ 30 kg/m² groups, education level (lower vs. higher), and household income (lower vs. higher) provided we have sufficient numbers within each subgroup ($n \geq 30$).

Descriptive analysis

The exploratory outcome measures will be discussed descriptively.

A Statistical Analysis Plan will be finalised before conducting the statistical analysis.

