Study Title: The impact of price promotions on purchases of confectionery and snacks: a randomised controlled trial in an experimental online supermarket study

Med IDREC Ref: R65010/RE005

Date 02/12/2021 Version 1.0

Summary of study

Participants (n=500) were asked to imagine they were buying snacks for a night in with 4 friends, with a budget of £5-£10. They were asked to select products from:

- Confectionery
- Biscuits and crackers
- Crisps, nuts and snacking fruit
- Cakes and tarts

They were randomised to one of two groups:

1. Promotions removed: No promotions present on any products
2. Promotions included: Promotions applied to a pre-determined percentage of food products (matching frequency/discount depth found on real online supermarket) within the target categories listed above.

Primary Analysis

Linear regression models will compare the total energy (kcal) purchased in the two groups. Any baseline variables (e.g. demographic characteristics) which appear to have been imbalanced between groups will be adjusted in the model. If no baseline characteristics are needed in models, then simpler t-tests will be considered. Non-parametric equivalents will be used should assumptions for parametric tests be violated.

Sensitivity analysis:

The primary analysis will be run including only participants who spent between £5 and £10 on products from the target categories (Confectionery; Biscuits and crackers; Crisps, nuts and snacking fruit; Cakes and tarts) will be included, to explore the impact for participants who had greater likelihood of being exposed to the promotional activity.

Secondary Outcomes

Linear regression models will compare the two groups on:

- a. total sugar (g, kcal, %E)
- b. total salt (g, kcal, %E)
- c. total saturated fat (SFA) (g, kcal, %E)

Secondary Analyses

1. *Including demographics:* Linear regression models will compare purchases in the two groups, stratified by demographic covariates including gender, age group, ethnic group (White vs Non-White), BMI (<30 and $\geq 30\text{kg}/\text{m}^2$) groups, education level (lower vs. higher), and household income (lower vs. higher) [provided we have sufficient numbers within each subgroup ($n \geq 30$)], with the following outcomes:
 - a. total energy (kcal)
 - b. total sugar (g, kcal, %E)
 - c. total salt (g, kcal, %E)
 - d. total SFA (g, kcal, %E)

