6. INTERVENTION

This study uses a bespoke virtual online supermarket shopping (OLS) platform, hosted by The University of Oxford, which emulates a real online supermarket for research purposes relating to food purchasing interventions (www.woodssupermarket.co.uk). The site is populated with approximately 23,000 current supermarket products drawn from foodDB (April 2019), a weekly updated database of food and drinks available for purchase in six UK online supermarkets (24).

Participants will be asked to imagine they are buying snacks for a night in with 4 friends, with a maximum limit of £10. They will be asked to select products from the following categories, which are aligned and named in the way items are presented in the store:

- Confectionery
- Biscuits and crackers
- Crisps, nuts and snacking fruit
- Cakes and tarts

The shopping task is estimated to take participants 10 minutes to complete. Participants will only be asked to complete the shopping task once. Participants will be provided with the following instructions:

“We would like you to do some online grocery shopping on a supermarket website. This is not a real supermarket, and you will not be asked to spend your own money.

We would like you to imagine you are buying snacks for a night in with 4 friends, up to a limit of £10. You should select products from the following categories:

- *Confectionery*
- *Biscuits and crackers*
- *Crisps, nuts and snacking fruit*
- *Cakes and tarts*

We would ask you not to select any additional items from your usual shopping list.

When doing your shopping, try to imagine you are doing your own grocery shopping and choose foods that you and your friends would eat. You should choose the things you normally buy or wouldn't mind eating.

To make sure you get your reward, please make sure you buy at least £5 worth of products within the suggested food categories”

Participants will be randomly allocated to one of the two following groups when shopping online:

1. Promotions removed: No promotions present on any of the products within the target food categories [confectionery; biscuits and crackers; crisps, nuts and snacking fruit; cakes and tarts] offered to participants when searching for products.

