2. Promotions included: Participants in this group will see a version of the website which will reproduce the types and frequency of promotions that can be found in any online supermarket, for example multi-buy offers and temporary price reductions will be applied to a pre-determined percentage of food products within the target categories [confectionery; biscuits and crackers; crisps, nuts and snacking fruit; cakes and tarts]. Promotions will be applied to match the current levels and types of promotions on the website of the largest UK retailer present in a specific week, shortly before the study launch.

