8.8. Discontinuation/Withdrawal of Participants from Study

Each participant has the right to withdraw from the study at any time. Participants will not be replaced as we will recruit sufficient sample size to allow for non-completion rate. Withdrawal from the study, based on the pre-defined completion criteria (section 9.2), will result in exclusion of the data for that participant from analysis.

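### The protocol drops baskets under £5 from analysis, a post-randomisation filter that promotions can shift in one arm only, and the SAP leaves the primary population unresolved

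*Combined protocol and SAP*

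**What the plan says.** Protocol 9.2 sets the criterion: "Completion of the task will be defined as spending at least £5 on products from the target categories". Protocol 8.8 gives its consequence: "Withdrawal from the study, based on the pre-defined completion criteria (section 9.2), will result in exclusion of the data for that participant from analysis". The same section treats such losses as covered by the sample size: "Participants will not be replaced as we will recruit sufficient sample size to allow for non-completion rate".

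The criterion is applied after allocation. Section 8.4 randomises participants and then sends them to the shop. Section 6 says that in the promotions arm "multi-buy offers and temporary price reductions will be applied to a pre-determined percentage of food products within the target categories", while the other arm sees no promotions in those categories. Participants are also told: "To make sure you get your reward, please make sure you buy at least £5 worth of products within the suggested food categories".

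The SAP (version 1.0, 02/12/2021) is later than protocol version 2.0 (24/09/2021). Its Primary Analysis says only: "Linear regression models will compare the total energy (kcal) purchased in the two groups". It gives no analysis population, completion criterion or exclusion rule. Its Sensitivity analysis reads: "The primary analysis will be run including only participants who spent between £5 and £10 on products from the target categories", and the stated purpose is "to explore the impact for participants who had greater likelihood of being exposed to the promotional activity".

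Neither document mentions an intention-to-treat or all-randomised population. Neither says whether spend is the shelf price or the amount paid after discount.

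**The concern.** Basket spend is a result of the task, closely tied to the kcal being compared. Price reductions lower the bill for a given basket, and multi-buys can raise it. Both occur in one arm only. A £5 cut-off can therefore retain different kinds of shopper in the two arms, and randomisation no longer protects the comparison. The direction depends on how shoppers respond and cannot be known in advance.

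The two documents also leave open whether the cut-off applies:

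- If the protocol rule governs, the primary result compares shoppers who spent at least £5. No planned analysis covers all submitted baskets, because the £5-£10 set filters on the same post-randomisation amount.
- If the SAP is meant to have no spend limit, the bias does not arise, but the SAP then conflicts with protocol 8.8 without saying so.

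**Working it through.** **Reading the text.** Section 8.8 points to the completion criterion in 9.2, and that criterion is a spend threshold. If 8.8 covered only people who leave the study, the pointer would have no function. The SAP's £5-£10 set implies a wider primary population, but the extra participants could be those under £5, those over £10, or both.

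**The plan's own allowance.** Section 9.1 gives a difference of 4.5, SD 15, 250 per arm, 5% alpha (taken as two-sided), 90% power and 10% attrition. With 250 × 0.9 = 225 per arm, the standard error is 15 × √(2/225) = 1.414 and power is Φ(4.5/1.414 − 1.96) = Φ(1.22) = 0.889, close to 90%. Losing 10% of participants is thus budgeted for in precision. That allowance does nothing about selection.

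**Size of the selection effect.** The documents give no spend distribution, promotion depth or top-up behaviour, so every input here is an assumption:

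- Shelf value of the basket is Normal, truncated to £0-£10. Case A has mean 7.5, SD 1.9 (10.4% under £5, a high case that treats all the planned attrition as baskets under £5). Case B has 8.0 and 1.5 (2.5% under). Case C has 8.5 and 1.2 (0.2% under).
- Kcal is proportional to shelf value, with lognormal noise (sigma 0.3) that affects only the standard errors.
- The effect is expressed as promotions against no promotions, so the planned effect is taken as +4.5%.
- Gap = effect among those paying at least £5, minus effect in all baskets, in percentage points of kcal.

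*Scenario 1, no material selection.* If shoppers pay the same amount and get more food, the gap is 0.0. If everyone pushed under £5 tops up, it is 0.0 to 0.1.

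*Scenario 2, same basket at a discounted price (true effect zero without top-up).* With saving d, a promotions-arm shopper is kept only if shelf value is at least 5/(1 − d). In case A the no-promotions mean among those kept is £7.50. The promotions-arm cut-offs and means are:

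- d = 5%: cut-off 5/0.95 = £5.26, mean £7.576, and 7.576/7.500 − 1 = +1.0%.
- d = 10%: cut-off £5.56, mean £7.673, giving +2.3%.
- d = 15%: cut-off £5.88, mean £7.794, giving +3.9%.

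| Case | No top-up, saving 5/10/15% | Half of those pushed under £5 top up |
|---|---|---|
| A | +1.0 / +2.3 / +3.9 | +0.5 / +1.1 / +1.9 |
| B | +0.4 / +1.1 / +2.0 | +0.2 / +0.5 / +1.0 |
| C | +0.1 / +0.2 / +0.5 | +0.0 / +0.1 / +0.2 |

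*Scenario 3, multi-buys that add food.* The shopper pays £x more and receives 1.5x of food (3-for-2), only if the bill stays within £10. Setting x so that the all-baskets effect is exactly +4.5% gives x = £0.22, £0.24 and £0.26 in A, B and C. Baskets just under £5 now enter the promotions arm, which lowers its mean. The filtered estimates are +3.5, +4.1 and +4.45, so the gaps are -1.0, -0.4 and -0.05. With buy-one-get-one-free (2x of food) they are -0.8, -0.3 and -0.04.

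No bill exceeds £10 in these scenarios, so the £5-£10 set gives the same gaps. If bills can pass £10, the two sets differ.

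**A second set of assumptions.** Shelf spend is Normal with SD £2, clipped to £0.50-£10, with identical baskets in both arms and savings of 5/10/20%. The apparent difference among those paying at least £5 is +1.6/+3.6/+9.0% at mean £6.50, +1.0/+2.3/+5.9% at £7.50 and +0.6/+1.2/+3.4% at £8.50. With everyone kept it is within 0.1% of zero.

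**The case against.** The strongest reply is that the SAP already has the right primary analysis. It is the later document, its primary analysis carries no spend limit, and participants are told not to exceed £10. If that cap is followed, the £5-£10 set is nearly the same as the at-least-£5 set, so the sensitivity analysis does real work only if the primary analysis includes baskets under £5. This is the more natural reading, and on it a clarifying sentence is enough. But the SAP does not withdraw 8.8, and neither document says the £10 limit is enforced.

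The size is also open to challenge, fairly:

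- The reward instruction and the payment for completing the task (12.4) may make baskets under £5 rare and topping up common.
- Promotions cover only some products, so a 10-15% saving across the basket needs heavy take-up.
- Case A counts all attrition as baskets under £5, although some participants may never submit one.
- Scenario 3 adds the same £x to every basket, which builds in a larger proportional effect in small baskets. With a proportional uplift (kcal +4.5%, bill +3%) the 3-for-2 gaps roughly halve, to -0.5, -0.2 and -0.03. The sign is unchanged.
- Against the standard error of about 3.0 to 3.5 points implied by the assumed baskets, only the +3.9 cell exceeds one standard error. Against the plan's own SD, 15 × √(2/250) = 1.34 points, four scenario 2 cells do (+2.3 and +3.9 in A and +2.0 in B without top-up, +1.9 in A with half top-up).

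The floor is pre-specified, told to both arms, and screens out inattentive shopping. Blinding of the statistician (8.5) limits choosing between the readings by result. None of this says which population is primary, or removes bias that the filter itself creates.

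**Conclusion.** The concern holds. Read together, protocol 8.8 and 9.2 filter the primary comparison on a post-randomisation amount that promotions can change in one arm only, and the SAP does not settle whether that rule stands.

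The size cannot be determined from the documents. In the main assumed cases the gap runs from -1.0 to +3.9 points against a planned 4.5%. In the second set of assumptions, with lower spend and deeper discounts, it reaches +9.0. It is about zero if few baskets fall near £5 or if shoppers top up. The sign depends on whether promotions mainly cut bills or mainly add purchases.

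This should be fixed before analysis. Confidence is medium, because the textual conflict is clear but the size rests wholly on assumed inputs.

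**What to change.** State one rule in protocol 8.8, protocol 9.2 and the SAP. The primary population is all randomised participants who submitted a basket, whatever they spent, analysed in the group to which they were randomised, except those who ask through the exit page (12.5) that their data not be kept. Then:

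- keep the at-least-£5 and £5-£10 sets as sensitivity analyses;
- define spend as before or after discount;
- report by arm the numbers with no basket, under £5 and over £10.

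The cost is one sentence in each of the three places, a price definition and a small table. The downside is that some very small or careless baskets enter the primary analysis. Using SE = CV × √(2/n), with n = 250 per arm for all baskets and 250 times the share at or above £5 for the filtered set:

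- Case A: 0.3872 × √(2/250) = 3.46 points against 0.3552 × √(2/224) = 3.36, a rise of 3.2% before rounding.
- Case B: a rise of 0.8%.
- Case C: a rise of 0.1%.

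Conditioning on having submitted a basket remains, which is why the count with no basket should be shown by arm.

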10. DATA MANAGEMENT

10.1. Access to Data

Direct access will be granted to authorised representatives from the University of Oxford for monitoring and/or audit of the study to ensure compliance with regulations.

10.2. Data Handling and Record Keeping

All study data will be captured in a password protected secure database. The participants will be identified by a unique study specific number and/or code in any database. Personal data will not be collected in this study. Research data and records will be retained for at least three years after publication or public release of the work of the research and reviewed thereafter.

11. QUALITY CONTROL AND QUALITY ASSURANCE PROCEDURES

The study will be conducted in accordance with the current approved protocol, relevant regulations and standard operating procedures.

12. ETHICAL AND REGULATORY CONSIDERATIONS

12.1. Declaration of Helsinki

The Investigator will ensure that this study is conducted in accordance with the principles of the Declaration of Helsinki.

12.2. Approvals

The protocol, informed consent form, participant information sheet and any proposed advertising material will be submitted to the ethical committee for approval.

The Investigator will submit and, where necessary, obtain approval from the above parties for all substantial amendments to the original approved documents.

12.3. Participant Confidentiality

All data collected by participants will be anonymous. The participants will be identified only a participant ID number on all study documents and any electronic database. All documents will be stored securely requiring password-protected access and will be only accessible by study staff and authorised personnel.

Privacy and confidentiality of data is particularly hard to manage in Internet-based research because as researchers we are not in control of online communication networks, leading to the risk of third-party interceptions. We will encourage the use of a secure link at the consent stage. Participants will be informed that we will not collect their IP addresses. As the data will be anonymised, it does not constitute personal data and the duties and obligations of the Data Protection Act do not apply. The research agencies will only share with the researchers a participant ID and no personal data.

12.4. Expenses and Benefits

Participants will be rewarded with £25p for the screening survey and £1.5 for completing the shopping task and survey.

12.5. Other Ethical Considerations

Internet based research issues

a) Authentication

The research agency who will recruit participants uses a number of mechanisms to authenticate responders such as checking for duplicate respondents by evaluating variables such as email address, matches across several demographic data, and device-related data through use of digital fingerprint technology.

b) Participant rights

Participants will be free to withdraw themselves and their data at any point in the research. During the shopping task, clicking on a clearly displayed “exit here” button will lead participants to a quick debrief page that will give them the option to confirm that they do not wish their data to be retained for the study purposes. Participants will be clearly informed before giving consent that anonymity makes withdrawal following completion of the study difficult.

13. FINANCE AND INSURANCE

13.1. Funding

The study is funded by the National Institute for Health Research (NIHR) Applied Research Collaborations (ARC Oxford).

13.2. Insurance

This is a simple online task and we cannot foresee any unintended or adverse effects due to participation. The University of Oxford maintains Public Liability and Professional Liability insurance that will operate in this respect.

14. PUBLICATION POLICY

[figure not shown]
The Investigators will be involved in reviewing drafts of the manuscripts, abstracts, press releases and any other publications arising from the study. Authors will acknowledge that the study was funded by the NIHR Oxford ARC. Authorship will be determined in accordance with the ICMJE guidelines and other contributors will be acknowledged. As we will not store the participants' contact details, we will not be able to disseminate the results directly to study participants. We will follow our dissemination plan to engage with public health agencies, the industry, the media, and the public.

16. APPENDIX A: STUDY FLOW CHART

17. APPENDIX B: SCHEDULE OF STUDY PROCEDURES

RECRUITMENT TEXT

The content of the recruitment text will be consistent with other emails sent to panel members but will contain the following text:

Survey topic: Health, Survey length: 10 minutes, Reward: £ xxx

Hi [Name],

We have a new survey available for you. By qualifying and completing this task, you will receive £xxx.

This study is being carried out by the University of Oxford. The study aims to investigate ways of helping people make healthier choices when they shop in an online supermarket. The purpose of this study is to explore how people shop for confectionery and snacks in an online supermarket. It will involve completing an online shopping study which should take no more than 10 minutes.

Before undertaking the task, you will be asked to read some detailed participant information, to confirm you are eligible, and confirm your consent to participate.

For further information and to take part go to [link to survey page (PIS and consent) and shopping website].

SCREENING QUESTIONS (Pre-shopping)

1. Age
 - Under 18 years old
 - 18 years old or over

2. Do you currently reside in the UK?
 - Yes
 - No

3. Are you fluent in English?
 - Yes
 - No

4. Do you have any dietary restrictions?
 - Vegan
 - Gluten-free
 - Sugar-free
 - Dairy/lactose-free
 - None
 - Rather not say

5. Are you the main (or shared) grocery shopper for the food that your household eats?

- Yes
- No

BASELINE MEASURES (Socio-demographic, shopping and health measures)

1. Demographic characteristics

- Gender
 - Male
 - Female
 - Other
 - Prefer not to say
- Age (years)
 - Free text (range of 18-99)
 - Prefer not to say
- Ethnicity (UK Census simplified)
 - White
 - Black
 - Asian
 - Mixed
 - Other
 - Prefer not to say
- Weight and height (in units chosen by participant).

2. Household income (total household income before tax)

- Below £15.5K
- Between £15.5K up to and including £25K
- Between £25K and £39K
- £40K or above

3. Household size – “How many people live at your house, including you?”

4. Highest educational level) - “What is the highest education qualification you have achieved?” (categories based on UK census categories)

- None
- Up to 4 GCSE's (Including 1-4 O Levels/CSE/GCSEs (any grades), Foundation Diploma, NVQ level 1, Foundation GNVQ or equivalents)
- 5 or more GCSE's or 1 A-level (Including 5+ GCSEs (Grades A*-C), 1 A Level/ 2-3 AS Levels, NVQ level 2, Intermediate GNVQ, City and Guilds Craft, BTEC First/General Diploma, RSA Diploma, Apprenticeship or equivalents)
- 2 or more A-levels (Including 2+ A Levels, 4+ AS Levels, NVQ Level 3, Advanced GNVQ, City and Guilds Advanced Craft, ONC, OND, BTEC National, RSA Advanced Diploma or equivalents)
- Bachelor's degree (Including BA, BSc, NVQ Level 4-5, HNC, HND, RSA Higher Diploma, BTEC Higher level or equivalents)

- Post-Graduate degree or qualification (Including Higher Degrees e.g. MA, PhD, PGCE, Professional qualifications e.g. teaching, nursing, accountancy or equivalents)

5. Regular shopping

“On average, how much do you spend on supermarket shopping per week?” (answer in £)

6. Online shopping experience

“How often, on average over the past year, have you shopped online for food or groceries to be delivered to you (e.g. Tesco.com, Ocado.com, mysupermarket.co.uk)?”

- Never or not in the last year
- 1-3 times in the last year
- 4-11 times in the last year
- 1-3 per month
- Once per week or more often.

POST-SHOPPING TASK PARTICIPANT SURVEY

1. “Did you see any promotions in the online supermarket you used in the shopping task today?”

- “Yes/No/Don’t know”

1A. “Do you usually buy products on promotion when you do your usual shopping?”

- Strongly agree
- Somewhat agree
- Indifferent
- Somewhat disagree
- Strongly disagree

1B. “Out of the two promotional strategies, product price reductions (e.g. save £1, reduced to 99p) or multi-buy offers (e.g. 3 for 2, buy-one-get-one-free), which is more likely to influence what you buy?”

- Price reductions
- Multi-buy offers

2. “When making a choice of foods or drinks to buy, what are the top 3 things that affect your decision?”

- Price
- Appearance
- Taste (preference)
- Habits
- Healthiness
- Convenience (to prepare or to consume)
- Special offers
- Organic
- Special diet e.g. gluten free, nut free
- Other (e.g. animal welfare, locally produced, packaging)

3. “The UK government is considering a policy to ban all promotions on high fat salt sugar products in supermarkets (both in-stores and online). To what extent would you support or oppose this policy?”

- Strongly support
- Support
- Somewhat support
- Neither support nor oppose
- Somewhat oppose
- Oppose
- Strongly oppose

3A. “For what reason did you give this answer?”

[FREE TEXT ANSWER]

4. “Is there anything else you’d like to tell us about your experience with this shopping task today?”
(Please do NOT include your name here).

[FREE TEXT ANSWER]

